9. PHARMACOKINETIC ANALYSES

The pharmacokinetic (PK) analyses will be based on the Pharmacokinetic population, unless otherwise specified.

Pharmacokinetic data from Part 1 of the study will be analyzed using standard non-compartmental methods, and combined data from Part 1 and Part 2 of the study will be analyzed in a population approach using nonlinear mixed effects modeling. Full details are presented in [Appendix 12](#): List of Data Displays.

9.1. Endpoint / Variables

9.1.1. Drug Concentration Measures

Refer to [Appendix 5](#): Data Display Standards & Handling Conventions (Section 16.5.3 Reporting Standards for Pharmacokinetic)

9.1.2. Derived Pharmacokinetic Parameters

9.1.2.1. Non-compartmental Analysis

- The pharmacokinetic parameters for Part 1 will be calculated by standard non-compartmental analysis according to current working practices and using Phoenix WinNonlin, version 6.3 or later.
- All calculations of non-compartmental parameters will be based on actual sampling times.
- Pharmacokinetic parameters described in [Table 7](#) will be determined from the Cycle 1 plasma concentration-time data in Part 1 of the study separately for each analyte, as data permit.

Table 7 Derived Pharmacokinetic Parameters

Parameter	Parameter Description
AUC(0-t)	Area under the concentration-time curve from time zero to the time of the last quantifiable concentration (C(t)) will be calculated using the linear trapezoidal rule for each incremental trapezoid and the log trapezoidal rule for each decremental trapezoid.
AUC(0-τ)	Area under the concentration-time curve during the dosing interval
AUC(0-∞)	Area under the concentration-time curve extrapolated to infinity will be calculated as: $AUC = AUC(0-t) + C(t) / \lambda_z$
%AUCex	The percentage of AUC (0-∞) obtained by extrapolation (%AUCex) will be calculated as: $[AUC(0-inf) - AUC(0-t)] / AUC(0-inf) \times 100$
Cmax	Maximum observed concentration, determined directly from the concentration-time data for each cycle
tmax	Time to reach Cmax, determined directly from the concentration-time data for each cycle
Cτ, Ctrough	Trough concentration prior to the next dose for each cycle

Parameter	Parameter Description
$t_{1/2}$	Apparent terminal half-life will be calculated as: $t_{1/2} = \ln 2 / \lambda_{z}$
t_{last}	Time of last observed quantifiable concentration
CL	Clearance
V _{ss}	Volume of distribution at steady state
λ_z , λ_{z}	Terminal phase rate constant
Ae(0-24)	Urinary recovery of cys-mcMMAF within the 24-h collection period will be calculated as: Urine cys-mcMMAF concentration x 24-h urine volume
Fe	Fraction of cys-mcMMAF dose excreted in the 24-h collection period will be calculated as: Ae(0-24) / cys-mcMMAF dose

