Serum (cytokines/chemokines)		X ¹⁹	X			X ¹⁹	At predose and EOI on D1 of each cycle	X	
Serum (anti-drug-antibodies)	X					X ²⁰	At the start of cycles 3 ²⁰ , 6 ²⁰ , 9 ²⁰ , 12 ²⁰ and 16 ²⁰	X	
Plasma-cfDNA	X							X	
Peripheral blood (flow for TBNK)	X ¹⁵					X ¹⁵	At the start of each cycle ¹⁵	X ¹⁵	
Serial Pharmacokinetics (blood)		X ²¹	X ²¹	X ²¹	X ²¹	X ²¹	C3D1 only ²¹	X ²²	
Urine PK	X ²³					X ²³	Day 1 of cycles 4 ²³ , 7 ²³ , 10 ²³ , 13 ²³ , 16 ²³		
Premedication if needed		X				X	At the start of each cycle		
GSK2857916 administration		X ²⁴				X ²⁴	X ²⁴		
Steroid eye drops		X ²⁵				X ²⁵	X ²⁵		
Adverse Events							Continuous		

Time and Events Table for Full Study (Cycle = 21 days)									
Study Assessments ¹	Screen ²	Day 1 C1	Day 2 C1	Day 8 C1	Day 15 C1	Day 1 C2	D1 of C3-C16	End of Study Treatment	3-Month Off-study Follow-up
Concomitant Medications	X	Continuous							
Survival Status									X ²⁶
Subsequent Treatment									X ²⁶

- Assessments scheduled on days of dosing should be done prior to drug administration, unless otherwise specified. All other assessments can be ± 3 days of scheduled occurrence unless otherwise specified.
- All Screening assessments must be performed within 14 days prior to first dose unless otherwise specified. Informed Consent must be signed before any study-specific assessments are performed.
- Screening examination to include BCVA (best-corrected visual acuity), slit lamp examination (with special focus on cornea), intraocular pressure, and dilated fundoscopic examination may be performed within 21 days prior to first dose.
- On-study exams to include BCVA (best-corrected visual acuity) and slit lamp examination (with special focus on cornea); window for exams is up to 3 days prior to dosing.
- On initial (first infusion) dosing day, vital signs must be assessed at pre-dose (within 30 minutes prior to SOI), +10 minutes and +30 minutes (±5 min) after SOI, EOI, and 1 hour post EOI. On subsequent dosing days, vital signs must be assessed at pre-dose (within 30 minutes prior to SOI), +30 minutes after SOI, and EOI. The Sentinel Subject must be observed for at least 24 hours post EOI. **On days where vital sign timepoints align with PK sampling timepoints, vital signs should be assessed prior to PK samples being drawn.**
- If completed within 72 hrs prior to the first dose, this assessment need not be repeated on Day 1 of Cycle 1. Refer to Table 15 of the protocol for comprehensive list of lab tests.

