19. Collect cytokines at predose (within 30 minutes prior to SOI) and EOI (± 5 min) (even when infusion is interrupted or halted) to assess allergic reaction)
20. All ADA samples will be collected prior to each infusion
21. PK samples to be taken (in all subjects) for both GSK2857916 and cys-mcMMAF measurement: C1D1 at pre-dose (within 30 minutes prior to SOI), 0.5 h after the start of the infusion (SOI) (± 5 min), at the end of infusion (EOI) just before EOI, 1 h after EOI, 3 h after EOI (± 5 min), 8 h after EOI (± 15 min), 24h after EOI (± 1 h) (Day 2); C1D8 1 sample; C1D15 1 sample; C2D1, at pre-dose (within 30 minutes prior to SOI) and at the EOI (just before EOI); C3D1 at pre-dose (within 30 minutes prior to SOI) and at the EOI (just before EOI).
22. Collect 1 PK sample at each subject's final visit.
23. Pre-specified amounts of urine will be collected for PK analysis from the 24 hour urine collection at Screening, C2D1, C4D1, C7D1, C10D1, C13D1, and C16D1. Refer to Section 7.4.2 of the protocol for details.
24. Study drug administration ± 3 day window only
25. Prophylaxis with prednisolone phosphate 1% or dexamethasone 0.1% 1 drop QID x 4 days starting 1 day prior to treatment
26. Record subject's survival status and whether subsequent treatment for disease was given. Subject does not need to come in for visit.

Abbreviations:

ADA = Antibody Drug Antibody; ALP = alkaline phosphatase; BCVA = best corrected visual acuity; BNP = B-type natriuretic peptide; C1D1 = Cycle 1 Day 1, etc.; cfDNA = Circulating free DNA; CK = creatinine kinase; CRP = C-reactive protein; EM = extramedullary; EOI = End of Infusion; FLC = free light chain; PD = Pharmacodynamics; PK = Pharmacokinetics; QID = 4 times a day; SOI = start of infusion; SPEP = serum protein electrophoresis; UPEP = urine protein electrophoresis

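### Ae(0-24) and Fe in SAP Table 7 do not fit the urine schedule: as scheduled, the 24-h collections precede dosing, so Fe is not urinary recovery of the dose

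*SAP*

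**What the plan says.** Section 9.1.2.1 states that the Table 7 parameters "will be determined from the Cycle 1 plasma concentration-time data in Part 1 of the study". Two of them are urinary:

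- The amount, labelled Ae(0-24), is described in these words: "Urinary recovery of cys-mcMMAF within the 24-h collection period will be calculated as: Urine cys-mcMMAF concentration x 24-h urine volume"
- The ratio built on that amount, labelled Fe, is described in these words: "Fraction of cys-mcMMAF dose excreted in the 24-h collection period will be calculated as: Ae(0-24) / cys-mcMMAF dose"

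Both are reported for Part 1. Section 16.12.10 lists a urine excretion summary (4.0130) and a listing (4.0140), and the listing's programming note puts Ae(0-24) and Fe in place of the shell's usual amount and rate columns.

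Sampling is set out in Section 16.2.2.1. Footnote 23 reads: "Pre-specified amounts of urine will be collected for PK analysis from the 24 hour urine collection at Screening, C2D1, C4D1, C7D1, C10D1, C13D1, and C16D1". It then adds: "Refer to Section 7.4.2 of the protocol for details". Footnote 1 gives the general rule: "Assessments scheduled on days of dosing should be done prior to drug administration, unless otherwise specified". The cycle is 21 days. Section 16.2.1 says that weekly dosing was not explored, so this is the schedule that applies.

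**The concern.** The label (0-24) suggests the first 24 hours after a dose, and dividing by a dose suggests the share of that dose recovered in urine. The schedule appears to supply neither. Screening urine contains no drug. The other collections fall on Day 1 of later cycles and, by the default rule, come before that day's infusion. Following the plan would then present a trough-day amount as 0-24 h recovery and divide it by a whole dose. A reader who takes Fe at face value would see very little urinary excretion, mainly because of when the urine was collected.

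Three smaller mismatches go with this:

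- Plasma data from Cycle 1 cannot yield a urine parameter.
- From Cycle 4 the urine may carry drug from several infusions while the divisor is one dose, and Table 7 does not say which dose.
- Section 2.2 describes cys-mcMMAF as a breakdown product, yet Table 7 does not say how a cys-mcMMAF dose is obtained.

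**Working it through.** The plan gives no recovery figure to reproduce, so the check has two parts: timing from the schedule, then size under assumed kinetics.

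**Timing**

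1. Urine PK visits are Screening, C2D1, C4D1, C7D1, C10D1, C13D1 and C16D1. None is marked on C1D1, C1D2, C1D8 or C1D15.
2. Footnote 23 names no post-dose time. The footnotes for vital signs (5), ECG (11), soluble BCMA (18), cytokines (19) and blood PK (21) all name end-of-infusion or later times where these are meant.
3. The same schedule has a 24-hour urine protein and albumin collection at Screening and at the start of each cycle from Cycle 2. The PK portion appears to come from this disease-assessment urine.
4. A 24-h collection finished before the C2D1 dose therefore covers day 21 − 1 = 20 to day 21 after the first infusion. With the ±3-day dosing window it lies somewhere between day 21 − 3 − 1 = 17 and day 21 + 3 = 24.

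**Size**

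The SAP gives no half-life, so every half-life below is an assumption.

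*Model A, single-exponential excretion after one dose.* With k = ln 2 / half-life, the share of the 21-day output falling in day 20-21 is [exp(−20k) − exp(−21k)] / [1 − exp(−21k)].

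| Half-life (days) | Share of interval | Understatement (1/share) |
|---|---|---|
| 5 | 0.0086 | 117-fold |
| 7 | 0.0149 | 67-fold |
| 12 | 0.0252 | 40-fold |
| 14 | 0.0278 | 36-fold |

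Shorter half-lives give smaller shares, for example 0.0021 at 3 days.

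*Model B, cys-mcMMAF formed from the conjugate and then eliminated.* With a = ln 2 / conjugate half-life and m = ln 2 / cys-mcMMAF half-life, the cumulative fraction is F(t) = 1 − [m·exp(−at) − a·exp(−mt)] / (m − a). The share of the interval is [F(21) − F(20)] / F(21). The ratio to the true first day is [F(21) − F(20)] / F(1).

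| Conjugate / cys-mcMMAF half-life (days) | Share of interval | Ratio to true 0-24 h |
|---|---|---|
| 3 / 0.25 | 0.0022 | 0.016 |
| 7 / 1 | 0.0178 | 0.57 |
| 12 / 1 | 0.0285 | 1.2 |
| 14 / 2.5 | 0.0380 | 3.5 |

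The largest share is 0.0380, an understatement of 1/0.0380 = 26-fold. Constant excretion over the interval would give 1/21 = 0.048, or 21-fold.

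*Carry-over.* With equal doses every 21 days, earlier infusions add to the trough-day amount. In the 14 / 2.5 case the day 20-21 amount is 0.0216 of one dose's eventual urinary output. By then the decline follows the conjugate, so the sum over all earlier doses is about 0.0216 / (1 − 2^(−21/14)) = 0.0216 / 0.646 = 0.033 of one dose's output. Carry-over blurs which dose Fe refers to but does not turn it into a recovery fraction.

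**The case against.** The strongest objection is that the SAP leaves the urine details to protocol Section 7.4.2, which is not among the documents at hand, and that footnote 1 yields wherever something else is specified. A reader might infer that the SAP proves no urine was ever collected after a dose. It does not. Pre-dose is the default reading, supported by the contrast with the other footnotes, and Section 7.4.2 could set a different time. Even then, Table 7 would need to state the interval.

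A second tempting inference is that Ae(0-24) understates true first-day recovery by a known factor. That needs excretion to begin at its peak at dosing. For a metabolite formed slowly from the conjugate the ratio runs from 0.016 to 3.5, so the trough-day amount can exceed the first-day amount. This objection stands in full.

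Third, Table 7 words both parameters as referring to the 24-h collection period, and the SAP nowhere calls Fe total renal recovery. The arithmetic is right for the quantity described. What remains at fault is the (0-24) label, the divisor and the interpretation they invite.

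Fourth, the consequence is limited. Urinary recovery is not among the example PK endpoints in Section 2.2, and no test, dose decision or model described in the SAP uses it. This also stands and sets the severity.

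**Conclusion.** The mismatch is real on the SAP's own schedule, and minor. Read by default, every on-treatment urine PK collection is a pre-dose day, and none is scheduled in the 24 h after an infusion. The label Ae(0-24) and a fraction of dose therefore do not describe what is collected. If Fe is read as urinary recovery of the dose, it is too low by about 20-fold or more: 21-fold at constant excretion, and 26-fold or more under every half-life assumed here (conjugate 3 to 14 days with cys-mcMMAF 0.25 to 2.5 days, or a single half-life of 1 to 14 days). This rests on pre-dose timing, the nominal 21-day interval and those assumed ranges. No direction is claimed against true 0-24 h recovery. Only descriptive displays 4.0130 and 4.0140 for Part 1 are affected.

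**What to change.** 1. Check protocol Section 7.4.2 and state in Table 7 when the 24-h collection starts and ends relative to dose.
2. Unless a collection truly starts at dosing, rename the amount *Ae over the 24-h pre-dose collection*, do not report Fe as a fraction of dose, and carry both changes into 4.0130 and 4.0140.
3. Correct the lead-in to Table 7 so that Cycle 1 plasma data is not given as the source of the urine parameters.
4. Optionally, report an approximate renal clearance at C2D1: amount in the collection / (pre-dose plasma cys-mcMMAF concentration × 24 h). Footnote 21 provides the pre-dose plasma sample at that visit. State that one trough value stands in for the 24-h average, and restrict it to subjects with quantifiable cys-mcMMAF. In the Part 1 schedule C2D1 is the only on-treatment dosing visit with both urine and scheduled plasma PK sampling.

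The cost is SAP wording, one parameter definition and two display notes. No new samples are needed. Fe would no longer be reported, and the optional clearance would rest on a single visit.

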9.2. Population of Interest

The primary pharmacokinetic analyses will be based on the “Pharmacokinetic” population, unless otherwise specified.

9.3. Statistical Analyses / Methods

Details of the planned displays are provided in [Appendix 12: List of Data Displays](#) and will be based on GSK Data Standards and statistical principles. Unless otherwise specified, endpoints / variables defined in Section 9.1 will be summarised using descriptive statistics, graphically presented (where appropriate) and listed.

9.3.1. Statistical Methodology Specification

The following pharmacokinetic statistical analyses will only be performed if sufficient data are available.

9.3.1.1. Exploratory assessment of dose proportionality:

The PK-dose relationship initially will be examined graphically by plotting AUC(0-∞), AUC(0-τ), and C_{max} as a function of the dose levels administered; AUC(0-t) may be used for cys-mcMMAF. Plots of PK parameters versus dose will be produced, with two plots for each PK parameter. The first will be on a linear scale, and the second will use the logarithmic scale for both axes.

In practice, at least three dose levels are required to assess dose proportionality. Hence, if more than two dose cohorts are required to reach MTD (or recommended dose based on available safety, PK, and response data), dose proportionality of GSK2857916, unbound antibody, total antibody, and cys-mcMMAF following administration in Cycle 1 will be evaluated, if data permit, using the power model.

Dose Proportionality Analysis
Endpoint(s)

 Log_e-transformed single dose PK parameters (AUC(0-∞), AUC(0-τ), and C_{max}; AUC(0-t) for cys-mcMMAF) will be investigated.
Model Specification

 Endpoints for each analyte will be separately analyzed using appropriate methods for GSK2857916 doses. Power Model 
 Dose proportionality of PK parameters AUC(0-∞), AUC(0-τ), and C_{max} (AUC(0-t) for cys-mcMMAF) will be assessed following single dose administration of GSK2857916 between 0.03 mg/kg and 4.6 mg/kg, using the power model as described below: $y = \alpha * \text{dose}^\beta$ where y denotes the PK parameter being analyzed and α depends on subject. Dose proportionality implies that β=1 and will be assessed by estimating β along with its 90% confidence interval. The exponent, β, in the power model will be estimated by regressing the log_e-transformed PK parameter on log_e-transformed dose. The power model will be fitted by restricted maximum likelihood (REML) using SAS Proc Mixed. A power model with only subject as a random effect power model will be fitted. The mean slope will be estimated from the power model and the corresponding 90% confidence interval calculated. If the 90% confidence interval for the slope regressing dose against exposure is contained within the interval (0.8, 1.25), the exposure will be considered to be dose proportional.
Model Checking & Diagnostics

 Refer to Section 9.3.2.
Model Results Presentation

 Power Model 
 The mean slope and the corresponding 90% confidence interval for each parameter will be produced in tabular format. Comparative plots of individual PK parameters will be generated by treatment on linear and semi-logarithmic scales. Supportive SAS output from statistical analysis will be generated.

9.3.1.2. Assessment of Accumulation Ratio:

To assess the extent of accumulation following GSK2857916 repeat dosing, the observed accumulation ratio (Ro) for GSK2857916, total antibody, unbound antibody, and cys-mcMMAF will be determined as ratio of C_{max} and C_{trough} at steady-state to C_{max} and C_{trough} after the first dose, respectively, adjusted for any change in GSK2857916 dose.

$$Ro (C_{max}) = C_{max} C_{xD1} / C_{max} C_{1D1};$$

x = 3, 5;

$$Ro (C_{trough}) = C_{trough} C_{xD1} / C_{trough} C_{1D1};$$

x = 3, 5;

Preliminary pharmacokinetic data indicate that the pharmacokinetics for the third consecutive dose given at the planned interval will be at steady state. Therefore, based

on the study design, subjects who meet one of the following criteria will be at steady state:

- Subjects who receive the same dose without delay or change for Cycles 1, 2, and 3 (i.e., with dosing delays of ≤ 3 days). In this case, Cycle 3 represents steady state. Accumulation ratios are calculated as Cycle 3/Cycle 1.
- Subjects who receive the same dose without delay or change to Cycle 5. Accumulation ratio = Cycle 5/Cycle 1.
- Subjects who have a dose reduction or two by Cycle 3, but then dose is maintained at the same level and interval through Cycle 5. Cycle 5 represents steady-state pharmacokinetics, but dose adjustment is needed. Dose adjustment: multiply C_{max}/C_{trough} values by the ratio (starting dose level/Cycle 3-5 dose level). Accumulation ratio = adjusted Cycle 5/Cycle 1.

For the purpose of accumulation ratio analysis, C_{max} is defined as the EOI concentration at each cycle.

Exploratory analysis might be performed considering the effect of dose delay on the ratio.

Accumulation Ratio Assessment (Part 1 and Part 2)
Endpoint(s)

 • Accumulation ratio (R_o). The observed accumulation ratio (R_o) will be calculated for each analyte by determining the ratio of C_{max} at steady state to C_{max} on Day 1 ($R_o(C_{max})$) and the ratio of C_{trough} at steady state to C_{trough} on Day 1 ($R_o(C_{trough})$).
Model Specification

 • A mixed effect model will be fitted for each parameter by actual dose at each cycle as fixed effect and subject as random effect. The model will be adjusted by actual dose and dose delay status in each cycle. The ratio will be calculated by back-transforming the difference between the Least Squares means. Using the pooled estimate of variance, 90% confidence intervals will be calculated for the difference and then back-transformed. • The Kenward & Roger degrees of freedom approach will be used.
Model Checking & Diagnostics

 • Refer to Section 9.3.2.
Model Results Presentation

 • Geometric least-squares means for each treatment, point estimates and associated 90% confidence intervals for the ratios for each parameter will be produced in tabular format. • Plots of mean Accumulation Ratio will be generated by dose group on linear and semi-logarithmic scales. • The accumulation ratio will be listed and summarized along with other PK parameters. • Supportive SAS output from statistical analysis will be generated.

9.3.1.3. Assessment of Analyte Ratios:

Following natural log-transformation, C_{max} and C_{tau} of ADC, unbound and total antibody, and cys-mcMMAF will be analysed using a mixed effects model with fixed effect terms for treatment, visit, and $\log(\text{body weight})$. Subject will be treated as a

random effect in the model. Point estimates and their associated 90% confidence intervals will be constructed for the differences of Cmax and Ctau in analytes and comparison with cys-mcMMAF at each cycle. The point estimates and their associated 90% confidence intervals then will be back-transformed to provide point estimates and 90% confidence intervals for the ratios of analytes to cys-mcMMAF at each cycle.

Ratio of analytes at each cycle versus cys-mcMMAF at Cycle X:

$$Ra (Cmax) = \frac{Cmax (ADC, unbound anti-body, total anti-body) Cycle X}{Cmax (cys-mcMMAF) Cycle X}$$

X = 1, 2, 3, 5;

$$Ra (Ctrough) = \frac{Ctrough (ADC, unbound anti-body, total anti-body) Cycle X}{Ctrough (cys-mcMMAF) Cycle X}$$

X = 1, 2, 3, 5;

For the purpose of analyte ratio analysis, Cmax is defined as the EOI concentration at each cycle, and Ctrough is defined as the concentration immediately prior to the next cycle dose.

To fit into the analysis model, the units of the analytes need to be converted from ng/mL or pg/mL to nM as below.

	Original unit	Operation	Converted unit
ADC	ng/mL	/152.1	nM
Total Antibody	ng/mL	/152.1	nM
Unbound Antibody	ng/mL	/152.1	nM
cys-mcMMAF	pg/mL	/1045	nM

Pharmacokinetic Statistical Analyses
Endpoint(s)

 Cmax, Ctau by analyte and cycle
Model Specification

 Repeated measures mixed effects analysis
Model Checking & Diagnostics

 Refer to Section 9.3.2
Model Results Presentation

 Graphical ratios at Cycle 1 Graphical ratio of analyte to cys-mcMMAF by cycle

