5. CONSIDERATIONS FOR DATA ANALYSES AND DATA HANDLING CONVENTIONS

5.1. Study Treatment & Sub-group Display Descriptors

Treatment Group Descriptions				
RandAll NG		Data Displays for Reporting		
Code	Description ^[1]	Description ^[2]	Data Display	Order in TLF
A	Active Treatment	GSK2857916 0.03 mg/kg (Part 1 MM)	0.03 mg/kg	1
		GSK2857916 0.06 mg/kg (Part 1 MM)	0.06 mg/kg	2
		GSK2857916 0.12 mg/kg (Part 1 MM)	0.12 mg/kg	3
		GSK2857916 0.24 mg/kg (Part 1 MM)	0.24 mg/kg	4
		GSK2857916 0.48 mg/kg (Part 1 MM)	0.48 mg/kg	5
		GSK2857916 0.96 mg/kg (Part 1 MM)	0.96 mg/kg	6
		GSK2857916 1.92 mg/kg (Part 1 MM)	1.92 mg/kg	7
		GSK2857916 2.50 mg/kg (Part 1 MM)	2.50 mg/kg	8
		GSK2857916 3.40 mg/kg (Part 1 MM)	3.40 mg/kg	9
		GSK2857916 4.60 mg/kg (Part 1 MM)	4.60 mg/kg	10
		GSK2857916 3.40 mg/kg (Part 2 MM)	3.40 MM	11
		GSK2857916 3.40 mg/kg (Part 2 NHL)	3.40 NHL	12

Notes:

^[1] This is a single-arm study and only active treatment is planned for the study.

^[2] Part 1: dose escalation phase; Part 2: Expansion Cohort; MM: multiple myeloma; NHL: Lymphoma.

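### The dose-proportionality rule applies a fixed (0.8, 1.25) window to the power-model slope, which over a 153-fold dose range is too loose to support the label it awards

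*SAP*

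**What the plan says.** The analysis comes under the heading "Exploratory assessment of dose proportionality" and, like the other PK modelling in section 9.3.1, is done only if there are enough data. The model is y = α·dose^β, fitted to Cycle 1 parameters after "single dose administration of GSK2857916 between 0.03 mg/kg and 4.6 mg/kg". The exponent "in the power model will be estimated by regressing the log_e-transformed PK parameter on log_e-transformed dose".

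Two statements govern the conclusion. The first is sound: "Dose proportionality implies that β=1 and will be assessed by estimating β along with its 90% confidence interval". The second turns the interval into a verdict: if the 90% interval for the "slope regressing dose against exposure is contained within the interval (0.8, 1.25), the exposure will be considered to be dose proportional".

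The SAP gives no reason for the limits and nowhere adjusts them to the dose range. The results are to be shown as the mean slope with its 90% interval. Mock shell PK_T1 in Appendix 13 likewise has columns for slope, standard error, degrees of freedom and interval, and none for an exposure ratio.

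**The concern.** In a log-log regression the slope is a unitless exponent. What a reader wants to know is how far dose-normalised exposure drifts between the lowest and the highest dose. Under the model that drift is r^(β−1), where r is the ratio of highest to lowest dose. The same slope is harmless over a two-fold range and substantial over a hundred-fold range, so a fixed window on β has no fixed meaning. The numbers 0.8 and 1.25 look natural as limits for an exposure ratio, but here they are applied to the exponent.

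At stake is a categorical statement, made for up to four analytes and several parameters. A false label of proportionality could be taken as support for the linear dose scaling used elsewhere in the SAP: the dose adjustment of accumulation ratios in section 9.3.1.2 and the dose-normalised concentrations in Appendix 9. The SAP does not make either conditional on this result.

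**Working it through.** The SAP states no implied exposure ratio, sample size or power for this rule, so there is no figure of its own to reproduce.

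**Inputs**
- Dose range: 0.03 to 4.6 mg/kg (section 9.3.1.1). The treatment table in section 5.1 has the same lowest and highest levels.
- Window for the slope: (0.8, 1.25), 90% interval (section 9.3.1.1).
- Placeholder standard errors on 17 df in mock shell PK_T1: 0.036 for the first AUC(0-∞) row and 0.057 for Cmax. These are layout values, not data, and serve only as an illustration.

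**Dose range.** r = 4.6/0.03 = 153.3, and ln r = 5.033.

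**Edges of the window.** The ratio of dose-normalised exposure, top to bottom dose, is r^(β−1).
- β = 0.80: 153.3^(−0.20) = 0.365, a 2.74-fold shortfall. Exposure rises 56-fold for a 153-fold dose.
- β = 1.25: 153.3^(0.25) = 3.52, a 3.52-fold excess. Exposure rises 540-fold.

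**Accepted point estimates.** The whole interval must fit inside the window, so the estimate must be at least one half-width from each edge.
- SE 0.036: half-width 0.063, so estimates from 0.863 to 1.187 pass. These imply up to a 2.0-fold shortfall (1/153.3^(−0.137)) or a 2.6-fold excess (153.3^(0.187)).
- SE 0.057: half-width 0.099, so estimates from 0.899 to 1.151 pass, implying up to 1.66-fold and 2.14-fold.

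**One row of the shell.** The placeholder Cmax slope of 0.92 with interval (0.82, 1.01) passes the rule. On the ratio scale it is 153.3^(−0.08) = 0.67, with interval 153.3^(−0.18) = 0.40 to 153.3^(0.01) = 1.05. A result labelled proportional would thus be compatible with a 2.5-fold shortfall (1/0.40).

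**Dependence on the range analysed.** Parameters are derived as data permit (section 9.1.2.1), so the lowest usable dose may be higher for some analytes. The edges of the window then imply:

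| Lowest dose (mg/kg) | r | Shortfall at β = 0.80 | Excess at β = 1.25 |
|---|---|---|---|
| 0.03 | 153.3 | 2.74-fold | 3.52-fold |
| 0.12 | 38.3 | 2.07-fold | 2.49-fold |
| 0.48 | 9.58 | 1.57-fold | 1.76-fold |
| 1.92 | 2.40 | 1.19-fold | 1.24-fold |

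**Scaled slope limits.** For a ratio tolerance (L, U), the slope limits are 1 + ln(L)/ln(r) to 1 + ln(U)/ln(r).
- 0.8 to 1.25 over the full range: 1 ± 0.2231/5.033 = (0.956, 1.044).
- 0.5 to 2 over the full range: 1 ± 0.6931/5.033 = (0.862, 1.138).
- 0.8 to 1.25 over 1.92 to 4.6 mg/kg: (0.745, 1.255).

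The plan's limits match a ratio tolerance of 0.8 to 1.25 only for ranges of about 3.05-fold (lower limit, 1.25^5) and 2.44-fold (upper limit, 1.25^4).

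**The case against.** The strongest reply is that little hangs on the label. The analysis is exploratory and conditional on sufficient data. Dose decisions rest on the 3+3 and N-CRM information and the totality of the data (section 3.1.1), and the expansion dose is already shown as 3.40 mg/kg in section 5.1. The PK profile is a secondary objective, but dose proportionality is not named among the endpoints in section 2.2. The slope and its interval are tabulated, so a reader can compute the ratio. This stands, and it sets the severity.

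Three stronger readings are tempting and are not supported.
- *That the rule accepts a result showing a 2.7-fold shortfall or a 3.5-fold excess.* Those are the edges of the window. No accepted point estimate reaches them.
- *That the rule would pass markedly non-linear kinetics, such as target-mediated clearance at low doses.* The SAP has no figures from which to show this. Curvature is a departure from a single-slope model, which slope limits of any width do not directly test. The SAP also plans linear and log-log plots, a scatter plot against Cycle 1 dose, residual checks with alternative models (section 9.3.2) and population PK modelling.
- *That the window is five times too wide and must become 0.956 to 1.044.* The factor of five comes from requiring 0.8 to 1.25 for the exposure ratio across the whole range, a tolerance the SAP does not state. Under 0.5 to 2 the upper half-width is 0.25 against 0.138, and the lower 0.20 against 0.138. The strict limits may also be out of reach: with the placeholder half-width of 0.063 against 0.044, even a slope of exactly 1 would fail.

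Over 1.92 to 4.6 mg/kg the plan's window is slightly tighter than a 0.8 to 1.25 ratio tolerance would require. The problem lies in its use over the full range.

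**Conclusion.** The concern holds in a limited form. A window of (0.8, 1.25) on the exponent, not scaled to a 153-fold range, cannot by itself support a statement that exposure is dose proportional over that range. Its edges correspond to exposure ratios of 0.37 and 3.5. Accepted estimates could still imply about a 2.0-fold shortfall or a 2.6-fold excess, if the actual precision resembles the placeholder in shell PK_T1. That precision is an assumption: a larger standard error shrinks these figures and a smaller one moves them towards the edges. The figures also assume that the full 0.03 to 4.6 mg/kg range is analysed. A narrower usable range reduces them, as the table shows.

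Severity is minor to moderate. The fault affects how a PK result is labelled. It does not touch the validity of the trial or any decision that the SAP describes.

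**What to change.** Amend the criterion in section 9.3.1.1 and the layout of Table 4.0150 (shell PK_T1):

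1. Beside the slope and its 90% CI, report r^(β−1) with its 90% CI, using the dose range actually analysed for each analyte and parameter. The ratio's limits follow directly from the slope's limits, so no new model is needed.
2. Base the proportionality statement on that ratio against a tolerance fixed before the analysis, with slope limits scaled as 1 + ln(L)/ln(r) to 1 + ln(U)/ln(r).
3. Have the sponsor choose and justify the tolerance. Over the full range, 0.8 to 1.25 gives 0.956 to 1.044, which may be unattainable with the Part 1 sample. A tolerance of 0.5 to 2 gives 0.862 to 1.138. With the placeholder half-width of 0.063, that could be met by a slope within 0.075 of 1 (0.138 − 0.063).
4. Optionally, report the same ratio over 1.92 to 4.6 mg/kg, where a 0.8 to 1.25 tolerance gives slope limits of 0.745 to 1.255. This needs a second, restricted fit, and the narrower spread of doses will tend to make its slope less precise.

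The cost is a revised sentence or two and one table column, plus the restricted fit if it is wanted. The downside is that proportionality will be concluded less often over the full range.
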